1.1. Synopsis

Protocol Title: A Phase 1/2, Open-Label, Single-Arm, Dose-Escalation and Dose-

Expansion Study of the Safety, Tolerability, Pharmacokinetic, and Antitumor Activity of E-602 as a Single Agent and in Combination with

Cemiplimab in Patients with Advanced Cancers

Rationale:

The sialidase moiety of E-602 cleaves off immunosuppressive sialoglycans from immune and tumor cells to enhance antitumor immunity. In preclinical studies, E-602 has been shown to enzymatically remove sialic acids from cell surface sialoglycans and functions as an immune checkpoint blocker by releasing sialoglycan-mediated immunosuppression of antitumor immune cells. E-602 has been shown to enhance immune responses to tumor cells through multiple aspects, including restoring the function of exhausted-like T cells, improving antigen-specific T-cell response, and enhancing dendritic cell (DC) priming and activation of naïve T-cells. In addition, E-602 has a wide safety margin, as it is not an immune agonist and therefore does not cause cytokine activation. In humans, E-602 is expected to have antitumor activities either as a single agent or in combination with an anti-programmed death-1 (PD-1)/programmed death ligand-1 (PD-L1) agent.

Objectives and Endpoints:

Objectives	Endpoints
Dose Escalation Phase (Phase 1)	
Primary	
 To evaluate the safety and tolerability of E-602 as monotherapy in subjects with advanced cancers. To evaluate the safety and tolerability of E-602 in combination with cemiplimab in subjects with advanced cancers. To determine the maximum tolerated dose (MTD) and/or recommended Phase 2 dose (RP2D) of E-602 as monotherapy. To determine the MTD and/or RP2D of E-602 in combination with cemiplimab. 	 Incidence of adverse events (AEs) and serious adverse events (SAEs) graded according to National Cancer Institute (NCI) Common Terminology Criteria for Adverse Events (CTCAE) v5.0. Incidence and nature of dose limiting toxicities (DLTs) within a modified 3+3 design. The MTD and/or RP2D based on occurrence of DLTs within a modified 3+3 design.
Secondary	
 To assess the pharmacokinetics (PK) of E-602 as monotherapy. To assess the PK of E-602 in combination with cemiplimab. To evaluate the immunogenicity of E-602 To evaluate preliminary antitumor activity of E-602 as monotherapy in subjects with advanced cancers. 	 Noncompartmental PK parameters of E-602 as monotherapy and in combination with cemiplimab, including the maximum plasma concentration (C_{max}) and area under the plasma concentration-time curve (AUC).

Protocol Number: PAL-E602-001
Version 8.0, 24 August 2023

- To evaluate preliminary antitumor activity of E-602 in combination with cemiplimab in subjects with advanced cancers.
- Number and percentage of subjects who develop detectable antidrug antibodies (ADA).
- Objective response rate (ORR) of confirmed complete response (CR) and partial response (PR) using Response Evaluation Criteria in Solid Tumors (RECIST) v1.1 and Immunotherapy Response Evaluation Criteria in Solid Tumors (iRECIST).
- Duration of response (DOR).
- Progression-free survival (PFS), defined as the time from the first dose to first evidence of radiographically detectable disease or death from any cause, whichever occurred first.
- Overall survival (OS).

Dose Expansion Phase (Phase 2)

Primary

- To evaluate the preliminary antitumor activity of E-602 as monotherapy in subjects with advanced cancers.
- To evaluate the preliminary antitumor activity of E-602 at the combination RP2D in combination with cemiplimab in subjects with advanced cancers.
- ORR of confirmed CR or PR.
- DOR of confirmed CR or PR.
- PFS.
- OS.

Secondary

[figure not shown]
- To evaluate the safety and tolerability of E-602 as monotherapy in subjects with advanced cancers.
- To evaluate the safety and tolerability of E-602 in combination with cemiplimab in subjects with advanced cancers.
- To assess the PK of E-602 as monotherapy.
- To assess the PK of E-602 in combination with cemiplimab.
- To evaluate the immunogenicity of E-602

[figure not shown]
- Incidence of AEs and SAEs graded according to NCI CTCAE v5.0.
- Noncompartmental PK parameters of E-602 as monotherapy and in combination with cemiplimab, including C_{max} and AUC.
- Number and percentage of subjects who develop detectable ADA.

Phase 1 and Phase 2

Exploratory

- To evaluate exploratory pharmacodynamic biomarkers of E-602 activity as monotherapy.
- To evaluate exploratory pharmacodynamic biomarkers of E-602 activity in combination with cemiplimab.
- Immune cell desialylation and activation using FACS
- Immune cell gene expression profiling (RNAseq; Phase 1 E-602 monotherapy only)
- Changes in cytokine levels
- Changes in circulating tumor DNA
- Changes in tumor desialylation by immunohistochemistry (IHC)

Overall Design:

This is a Phase 1/2, first-in-human (FIH), open-label, dose escalation and dose expansion study of E-602, administered as a single agent and in combination with cemiplimab, to evaluate the safety, tolerability, PK, pharmacodynamics, and antitumor activity in subjects with advanced cancers.

Phase 1: Dose Escalation, Monotherapy and Combination Therapy

Phase 1 of the study consists of 5 planned dose escalation cohorts of E-602 as a monotherapy and 2 planned dose escalation cohorts of E-602 in combination with cemiplimab. Phase 1 monotherapy will treat eligible subjects with melanoma, ovarian cancer, non-small cell lung cancer (NSCLC), colorectal cancer, pancreatic cancer, breast cancer, gastric/esophagogastric junction (EGJ) cancer, head and neck cancer, or urothelial cancer. Phase 1 combination with cemiplimab will treat eligible subjects with melanoma, NSCLC, gastric/EGJ cancer, head and neck cancer or urothelial carcinoma. The safety of the dose regimens will be evaluated to identify the maximum tolerated dose (MTD) and recommended Phase 2 dose (RP2D) to be used during Phase 2.

The cohorts of E-602 monotherapy will receive E-602 at the doses of 1, 3, 10, 20 and 30 mg/kg, respectively, via intravenous (IV) infusion once a week. Intermediate dosing cohorts may be added in Phase 1. The first subject dosed in a cohort will be a sentinel subject, with at least 24 hours until any subsequent subjects are dosed in the cohort. No intrasubject dose escalation of E-602 will be permitted.

The cohorts of E-602 in combination with cemiplimab will be initiated at dose level(s) that have previously completed DLT assessments (Cycle 1) as monotherapy. Intermediate dosing cohorts may be added in Phase 1. Subjects in the combination cohorts will receive 20 mg/kg E-602 IV once a week (additional dose levels to be determined) and 350 mg cemiplimab IV once every 3 weeks. The first subject dosed in a cohort will be a sentinel subject, with at least 24 hours until any subsequent subjects are dosed in the cohort. No intrasubject dose escalation of E-602 will be permitted.

Each treatment cycle consists of 21 days. E-602 will be administered on Days 1, 8, and 15 of each cycle. Cemiplimab, if given, will be administered on Day 1 of each cycle. When the cemiplimab combination is administered, cemiplimab should be administered first and E-602 administered at least 30 minutes after the cemiplimab infusion is completed. Subjects receiving ≥10 mg/kg of E-602 as monotherapy or in combination with cemiplimab should receive premedication including antihistamines and acetaminophen as indicated in the Pharmacy Manual. Corticosteroids should be used as premedication for subjects with previous infusion reaction(s) to E-602 as indicated in the Pharmacy Manual (see Pharmacy Manual, Section 10.5).

Dose escalation guidelines for all Phase 1 dose cohorts will utilize a modified 3+3 design. Assessments of DLTs will occur during Cycle 1 (defined as a subject receiving 3 doses of E-602 for monotherapy cohorts and 3 doses of E-602 and 1 dose of cemiplimab for combination therapy cohorts) for all dose cohorts. Safety monitoring for immune-related toxicities will continue for all subjects for 90 days after treatment discontinuation unless a subsequent cancer therapy is started. All available data will be taken into consideration in selecting the RP2D.

E-602 dose escalation will continue until the MTD is exceeded, unacceptable toxicity is reached, or the RP2D is determined. The Sponsor may terminate dose escalation at a RP2D prior to reaching the MTD based on emerging PK, pharmacodynamic, and safety data.

Any Phase 1 cohort may be backfilled at the judgement of the Sponsor, up to a total of 15 subjects in the dose cohort (dose escalation and backfill) as needed to obtain additional safety, PK and pharmacodynamic data at a particular dose level.

In addition to DLTs, subjects will be evaluated for safety and tumor response as well as PK and pharmacodynamics, as listed in the Schedule of Activities (SoA) in Section 1.3.

Phase 2: Dose Expansion, Monotherapy and Combination Therapy

Phase 2 consists of dose expansion disease cohorts in subjects with 3 types of advanced tumors: melanoma, NSCLC, and the third type to be determined (ovarian, colorectal, pancreatic, breast, gastric/EGJ, head and neck, or urothelial) based on available data including the Phase 1 results. Phase 2 of the study will employ a 2-stage design, as outlined in Section 9.4. Each disease cohort will be analyzed separately. The E-602 dose(s), i.e., RP2D(s), chosen based on Phase 1 data will be used. E-602 as monotherapy and in combination with cemiplimab will be evaluated separately.

Subjects will be evaluated for safety and tumor response as well as PK and pharmacodynamics, as listed in the Schedule of Activities (SoA) in Section 1.3.

Treatment Discontinuation Criteria

Subjects will permanently discontinue study treatment for any of the following:

- Progressive disease (confirmed PD for subjects who continued treatment beyond PD, see Section 4.1.2)
- Initiation of alternative cancer therapy
- Unacceptable toxicity including permanent discontinuation criteria defined in Section 6.5
- Subject's decision to discontinue treatment
- Withdrawal of consent
- Investigator's decision to discontinue treatment
- Sponsor's decision to discontinue treatment
- Inability of the subject to comply with the requirements of the study
- Completion of maximum treatment duration of 1 year from Cycle 1 Day 1

Treatment Beyond Disease Progression

Treatment beyond PD will be allowed as per iRECIST guidelines. The following criteria must be met for continued use of the study treatment beyond PD:

• Absence of symptoms and signs indicating clinically significant progression of disease

- No decline in the Eastern Cooperative Oncology Group (ECOG) performance status
- Absence of symptomatic rapid disease progression requiring urgent medical intervention (e.g., symptomatic pleural effusion, spinal cord compression).

At the time of radiographic progression of disease, a subject will be reconsented with emphasis on the FDA-approved therapy and potential clinical benefit that the subject may be foregoing to continue treatment.

Post-treatment Follow-up

For subjects who complete the 1-year treatment, an end-of-treatment (EOT) visit will be conducted, and subjects will return for safety follow-up visits 30 and 90 days after the last dose of study treatment to monitor for safety, including late immune-related toxicities. If prior to completing the 90-day safety follow-up period a subject begins a new cancer treatment, no further safety follow-up is required.

For subjects who discontinue treatment early, an EOT visit will be conducted, and subjects will return for safety follow-up visits 30 and 90 days after the last dose of study treatment. If prior to completing the 90-day safety follow-up period a subject begins a new cancer treatment, no further safety follow-up is required. These subjects will continue to be contacted once every 3 months for disease and survival status through approximately 15 months after the first dose of the study treatment unless the subject has died or withdrawn consent.

Phase 1 Dose-escalation Guidelines:

The following modified 3+3 guidelines will be employed on the basis of the number of DLTs observed during Cycle 1 (3 doses of E-602 administered for monotherapy cohorts and 3 doses of E-602 and 1 dose of cemiplimab administered for combination therapy cohorts):

- Each dose level cohort will treat 3-6 subjects. At each dose level, at least 3 subjects must be DLT-evaluable prior to dose escalation.
- If 0 subjects experience a DLT, the next cohort will be treated at the next higher dose level.
- If only 1 subject experiences a DLT in 6 DLT-evaluable subjects, the next cohort will be treated at the next higher dose level.
- If 2 or more subjects in any cohort experience a DLT, the MTD will have been exceeded and no further subjects will be treated at this or higher dose levels. Additional subjects will be treated at the next lower dose level if needed to have at least 6 subjects treated at that prior dose level. If at least 6 subjects were previously treated at the prior dose level, that prior dose level will be considered the MTD.

Dose-Limiting Toxicity (DLT) Definition:

The DLT window of observation for the purposes of dose escalation will be Cycle 1 defined as a subject receiving 3 doses of E-602 for monotherapy cohorts and 3 doses of E-602 and 1 dose of cemiplimab for combination therapy cohorts. Any of the following events will meet the definition of a DLT if assessed by the investigator to be possibly, probably, or definitely related to study treatment:

- Any death not clearly due to the underlying disease or extraneous causes
- Hy's law:

- Protocol Number: PAL-E602-001 Version 8.0, 24 August 2023
- Aspartate aminotransferase (AST) or alanine aminotransferase (ALT) >3×the upper limit of normal (ULN) AND
- Total bilirubin >2×ULN AND
- o Alkaline phosphatase <2×ULN AND
- No other reason for liver injury
- Neutropenic fever
- Any Grade \geq 3 non-hematologic toxicity (with exceptions noted below)
- Grade 4 neutropenia or thrombocytopenia >7 days
- Grade 3 thrombocytopenia with bleeding
- Grade 4 vomiting or diarrhea of any duration
- Grade 3 fatigue ≥7 days
- Grade ≥3 electrolyte abnormality that lasts >72 hours, unless the subject has clinical symptoms, in which case all Grade ≥3 electrolyte abnormality regardless of duration will be a DLT.
- For subjects with hepatic metastases, AST or ALT >8×ULN or AST or ALT >5×ULN for ≥14 days
- Recurrent Grade 3 infusion-related reaction despite pre-medication
- Grade 4 infusion-related reaction on the first occurrence
- Dose delay of >14 days for the study treatment due to an AE

However, the following AEs are NOT considered a DLT:

- Hematologic toxicity:
 - o Grade 3 anemia
 - o Grade 3 lymphopenia
 - Grade 3 or 4 neutropenia that is not associated with clinical sequelae and lasts <7 days
 - o Grade 3 or 4 thrombocytopenia without bleeding
- Cardiovascular toxicity:
 - o Grade 3 hypertension
- Other toxicities:
 - o Grade 3 fatigue lasting <7 days
 - o Grade 3 nausea/vomiting or diarrhea for less than 72 hours with adequate antiemetic and other supportive care
 - Grade 3 or higher electrolyte abnormality that lasts up to 72 hours, is not clinically complicated and resolves spontaneously or responds to conventional medical interventions
 - Grade 3 or higher amylase or lipase that is not associated with symptoms or clinical manifestations of pancreatitis
 - o Isolated Grade 3 infusion reaction
 - AEs that are clearly and incontrovertibly due to disease progression or extraneous causes.

Subjects treated in the Phase 1 dose escalation part of the study will discontinue treatment if he/she experience DLT(s) during Cycle 1.

Brief Summary:

The purpose of this study is to evaluate the safety, tolerability, preliminary efficacy, PK and pharmacodynamics of E-602, as a single agent or in combination with cemiplimab, for the treatment of subjects with advanced tumors. A maximum tolerated dose (MTD) and/or a recommended Phase 2 dose (RP2D) will be determined during Phase 1 to facilitate the conduct of Phase 2.

Study details include:

- Study duration: approximately 2 years from screening of the first subject to the last visit of the last subject (end of study).
- Treatment duration for individual subjects:
 - o Screening period: up to 4 weeks before Cycle 1 Day 1
 - o Treatment period: up to 1 year from Cycle 1 Day 1 regardless of treatment delays
 - o Follow-up period: up to approximately 15 months from Cycle 1 Day 1
- Visit frequency: approximately up to 7 visits in Cycle 1; up to 5 visits in Cycle 2 and from Cycle 3 onward, weekly visits in each 21-day cycle.

Number of Subjects:

The planned total number of subjects to be treated in Phase 1 of the study is up to 87 subjects including up to 42 subjects in dose escalation and 45 subjects in backfilled cohorts. The planned total number of subjects to be treated in Phase 2 of the study is up to 186 subjects.

Total study treatment is up to 273 subjects.

Treatment Groups and Durations:

Phase 1 Treatment (Planned):

Five escalating dose cohorts of E-602 monotherapy and 2 escalating dose cohorts of combination therapy will be treated.

Cohort	Number of Subjects ^a	Dose of E-602	Frequency of E-602	Dose of Cemiplimab	Frequency of Cemiplimab
101	3 – 6	1 mg/kg	once a week	n/a	n/a
102	3 – 6	3 mg/kg	once a week	n/a	n/a
103	3 – 6	10 mg/kg	once a week	n/a	n/a
104	3 – 6	20 mg/kg	once a week	n/a	n/a
105	3 – 6	30 mg/kg	once a week	n/a	n/a
111	3 – 6	20 mg/kg	once a week	350 mg	once every 3 weeks
112	3 – 6	to be determined	once a week	350 mg	once every 3 weeks

^a Phase 1 cohorts may be backfilled to a maximum of 15 subjects.

The dose for E-602 in the combination therapy cohorts will be initiated at dose level(s) that have previously completed dosing and DLT assessments (Cycle 1) as monotherapy.

Dose modifications will be made according to the protocol (Section 6.5).

Phase 2 Treatment (Planned):

Subjects in Phase 2 will receive the following treatment:

Cohort	Number of Subjects	Advanced Disease	Dose of E-602	Frequency of E-602	Dose of Cemiplimab	Frequency of Cemiplimab
201	16 – 31	melanoma	monotherapy RP2D	once a week	n/a	n/a
202	16 – 31	NSCLC	monotherapy RP2D	once a week	n/a	n/a
203	16 – 31	TBDa	monotherapy RP2D	once a week	n/a	n/a
211	16 – 31	melanoma	combination RP2D	once a week	350 mg	once every 3 weeks
212	16 – 31	NSCLC	combination RP2D	once a week	350 mg	once every 3 weeks
213	16 – 31	TBD ^a	combination RP2D	once a week	350 mg	once every 3 weeks

^a The third cohort will treat subjects with one of ovarian, colorectal, pancreatic, breast, gastric/EGJ, head and neck, or urothelial cancers based on available data including the Phase 1 results.

[figure not shown]
Duration of Treatment:

The maximum duration of treatment for each subject will be 1 year, regardless of treatment delays.

Safety Data Review Committee

A Safety Data Review Committee (SDRC) consisting of the principal investigators and members of the Sponsor will be formed and will meet regularly to review ongoing safety data. The committee will oversee subject safety and make recommendations to the Sponsor for all cohort dosing and dose escalation decisions.

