- 9. Vital signs (pulse, body temperature, blood pressure, and oxygen saturation via pulse oximetry) should be obtained while breathing room air. Vital signs should be obtained at screening and on Cycle 1 Day 1 (predose and 1 (± 15 minutes), 2 (± 15 minutes), 4 (± 30 minutes), and 6 hours (± 30 minutes) after the start of E-602 infusion), Cycle 1 Day 8 (predose), Cycle 2 Day 1 (predose and 1 (± 15 minutes), 2 (± 15 minutes), 4 (± 30 minutes) and 6 hours (± 30 minutes) after the start of E-602 infusion), and predose at all other visits as noted.
- 10. Medical history includes cancer history including PD-L1 and tumor molecular mutation status, previous cancer therapies, review of systems, past and current medical conditions.
- 11. See Appendix 10.2 for the laboratory tests required. Cycle 1 Day 1 laboratory tests may be performed up to 72 hours prior to Day 1 to ensure results are available for review prior to dosing. Thyroid panel is required every other cycle, beginning with Cycle 1 (e.g., Cycle 1 Day 1, Cycle 3 Day 1, Cycle 5 Day 1, etc.).
- 12. Plasma samples for E-602 concentrations will be collected at time points described in Section 8.4. An unscheduled plasma PK sample should be collected in the event of an infusion related reaction.

- Protocol Number: PAL-E602-001 Version 8.0, 24 August 2023
- 13. Plasma samples for ADA analysis will be collected pre-dose. An unscheduled plasma ADA sample should be collected in the event of an infusion related reaction.
- 14. Either serum or urine pregnancy test is allowed. The choice of test is at the investigator's discretion.
- 15. Physical examination will include, at a minimum, the assessment of cardiovascular, respiratory, gastrointestinal, dermatological and neurological systems along with the lymph nodes and liver. Physical examination should be performed during screening, within 72 hours of or on Cycle 1 Day 1 and on Day 1 of each subsequent cycle.

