10.2. Appendix 2: Clinical Laboratory Tests

The tests detailed in Table 7 will be performed by the local laboratory.

Protocol-specific requirements for inclusion or exclusion of subjects are detailed in Section 5 of the protocol.

Additional tests may be performed at any time during the study as deemed necessary by the investigator or required by local regulations.

Table 7 Protocol-required safety laboratory tests

Laboratory Tests		Paran	neters		
Hematology	hemoglobin hematocrit	RBC indices: mean corpuscular v	olume	White blood cell (WBC) count with differential	
	platelet count (absolute)	(MCV)		(absolute): neutrophils lymphocytes monocytes eosinophils basophils	
Chemistry	Blood urea nitrogen (BUN) creatinine uric acid ^a lactate dehydrogenase (LDH) ^b Glucose	chloride sodium potassium bicarbonate calcium ^c magnesium ^c phosphorus ^c	aspartate aminotransferase (AST) alanine aminotransferase (ALT) total bilirubin alkaline phosphatase (ALP)		albumin ^c lipase ^c amylase ^c
Routine urinalysis	Specific gravity, pH, glucose, protein, blood, ketones, bilirubin, urobilinogen (if available), nitrite, leukocyte esterase by dipstick Microscopic examination (if blood or protein is abnormal)				
Pregnancy testing	serum or urine human chorionic gonadotropin (hCG) pregnancy test (as needed for women of childbearing potential), choice of test at the investigator's discretion				
Thyroid Panel		ing hormone (TSF (FT3), and Free thyro		•	e (T3) or Free

Other screening tests

- Follicle-stimulating hormone and estradiol (as needed in women of nonchildbearing potential only)
- Coagulation: prothrombin time (PT), activated partial thromboplastin (aPTT), International Normalized Ratio (INR)

Safety laboratory tests including pregnancy test for Cycle 1 Day 1 may be collected up to 72 hours prior to Day 1 to ensure results are available for review prior to dosing on Day 1. For all other dosing days, serum electrolytes, ALT/AST and hematology test results need to be reviewed prior to dosing.

Investigators must document their review of each laboratory safety report.

^aTest should be performed at screening only.

^bTest should be performed at screening and each restaging visit (Cycle 4 Day 1, Cycle 7 Day 1, etc.).

^cTest should be performed at screening and Day 1 of each cycle.

10.3. Appendix 3: AEs and SAEs: Definitions and Procedures for Recording, Evaluating, Follow-up, and Reporting

Protocol Number: PAL-E602-001

Version 8.0, 24 August 2023

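### Calcium, magnesium and phosphorus have no scheduled post-dose test inside the DLT window, although the electrolyte DLT criterion exempts none of them

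*Protocol*

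**What the plan says.** **DLT criterion.** Protocol Section 1.1 (repeated in Section 4.1.5) lists among the DLTs, when the investigator judges the event possibly, probably or definitely related, a "Grade ≥3 electrolyte abnormality that lasts >72 hours, unless the subject has clinical symptoms". With symptoms, duration no longer matters. The list of exceptions has the counterpart: a "Grade 3 or higher electrolyte abnormality that lasts up to 72 hours, is not clinically complicated" is not a DLT. Neither entry names or exempts any particular electrolyte.

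**Window.** "The DLT window of observation for the purposes of dose escalation will be Cycle 1". "Each treatment cycle consists of 21 days", and "E-602 will be administered on Days 1, 8, and 15 of each cycle".

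**Test schedule.** The chemistry row of both Schedules of Activities (Sections 1.3.1 and 1.3.2) marks Days 1, 8 and 15 of Cycle 1, but its footnote 11 sends the reader elsewhere for content: "See Appendix 10.2 for the laboratory tests required". In that appendix, Table 7 lists "calcium ^c magnesium ^c phosphorus ^c", and footnote c restricts these tests to the screening visit and the first day of every cycle. Sodium, potassium, chloride and bicarbonate carry no footnote.

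**Pre-dose review.** The text under Table 7 adds that, on dosing days other than Cycle 1 Day 1, "serum electrolytes, ALT/AST and hematology test results need to be reviewed prior to dosing". It does not say which electrolytes are meant.

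**The concern.** A toxicity criterion can only be scored on analytes that are measured while the criterion applies. Here the criterion reaches every electrolyte, while the schedule for three of the seven listed in Table 7 appears to stop before the first dose and resume after the window has closed.

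DLT incidence is a Phase 1 primary endpoint and decides whether the next cohort opens. If a qualifying abnormality is not seen, the subject enters the DLT Evaluable Set as DLT-free and the dose level may be cleared on an incomplete count. Sections 4.1.5 and 7.1 also take a dose-escalation subject with a Cycle 1 DLT off treatment, so an unseen event means that the protocol's own rule is not applied.

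**Working it through.** The plan states no figure for this point. The main check compares the schedule with the window and needs no assumption.

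**1. Scheduled draws in Cycle 1**

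| Analytes | Screening / Day 1 | Day 8 | Day 15 | Post-dose draws in window |
|---|---|---|---|---|
| Sodium, potassium, chloride, bicarbonate | yes | yes | yes | 2 |
| Calcium, magnesium, phosphorus (footnote c) | yes | no | no | 0 |

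The Cycle 1 Day 1 sample precedes dosing: SoA footnote 11 allows it up to 72 hours early, and Section 6.1 places assessments before the dose. The next footnote c sample is Cycle 2 Day 1, nominally Day 22, after the 21-day window.

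**2. Gap between draws**

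- Footnote c analytes: 21 × 24 = 504 hours. The range is (21 − 2) × 24 = 456 hours, if Cycle 2 Day 1 is two days early, to (21 + 2 + 3) × 24 = 624 hours, if it is two days late and the first sample was 72 hours early.
- Unfootnoted electrolytes: 7 × 24 = 168 hours.
- Criterion: 72 hours.

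**3. The pre-dose review sentence, read both ways**

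- If it includes calcium, magnesium and phosphorus, it calls for results before the Day 8 and Day 15 doses that footnote c does not schedule.
- If it means only the four unfootnoted electrolytes, it agrees with footnote c, but the DLT criterion then covers three analytes that the schedule does not observe in the window.

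**4. Illustration of size (assumptions, not plan figures)**

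Assume onset uniform over the 21 days and an abnormality lasting L days (L ≤ 7). The chance that it overlaps a Day 8 or Day 15 draw is 2L/21. The chance that it overlaps the Cycle 2 Day 1 draw is L/21. Under footnote c the in-window chance is 0.

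Assume further that such events are the only DLTs, at a true rate of 30%, that every overlapped event is then scored, and that a cohort starts with 3 subjects and expands to 6 after one DLT. With observed rate q, escalation follows 0 of 3 or 1 of 6:

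P(escalate) = (1 − q)³ + 3q(1 − q)² × (1 − q)³

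| L | Overlap, Day 8 or 15 | q = 0.30 × overlap | P(escalate) | Overlap, Cycle 2 Day 1 |
|---|---|---|---|---|
| 3 days | 6/21 = 29% | 0.086 | 0.764 + 0.164 = 0.93 | 3/21 = 14% |
| 5 days | 10/21 = 48% | 0.143 | 0.630 + 0.198 = 0.83 | 5/21 = 24% |
| 7 days | 14/21 = 67% | 0.200 | 0.512 + 0.197 = 0.71 | 7/21 = 33% |
| none seen | 0% | 0 | 1.00 | – |

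The 3-day row lies exactly at 72 hours, so it is the lower edge of what the criterion counts.

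**The case against.** The strongest reply is that the pre-dose review sentence already closes the gap: if serum electrolytes is read broadly, current values for all seven are needed before each dose. That reading is possible, so a total blind spot is not proven. But the sentence concerns review and lists no analytes, whereas footnote c sets the timing of these three explicitly. The ambiguity still has to be resolved. Equally, a reader might infer that the two texts flatly contradict each other. They do so only under the broad reading.

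Second, other tests may find the abnormality. Section 8 and Appendix 2 allow unscheduled and additional tests, so symptomatic cases are not blocked. The Cycle 2 Day 1 draw may show an abnormality still present, so it would be wrong to say that the schedule can never find one. This part of the objection stands. It narrows the gap to asymptomatic abnormalities, which give no prompt for an extra test. The Cycle 2 Day 1 value falls after the window, and a single value gives no duration.

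Third, the affected events may be rare. The animal toxicology summary (Section 2.2.1.3) reports only minimal liver-enzyme changes, and Section 4.3.1 reports no DLTs up to 10 mg/kg. Nothing in the documents supports 30% as an expected rate. At a true rate of 10%, even complete detection gives an escalation probability of 0.729 + 0.177 = 0.91. The illustration shows direction and scale under its assumptions. It is not a forecast.

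**Conclusion.** The point holds for calcium, magnesium and phosphorus. Under footnote c they have no scheduled post-dose test inside Cycle 1, and no other passage clearly supplies one. Related, asymptomatic abnormalities of Grade 3 or higher that last beyond 72 hours can therefore be missed and the subject counted as DLT-free. That conclusion rests on the schedule alone. The probabilities also depend on uniform onset, the chosen durations and the 30% rate.

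Three stronger readings are not supported:

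- **All electrolytes are unobserved.** Four of the seven are drawn on Days 8 and 15, although a 168-hour gap does not by itself establish a duration above 72 hours for them either.
- **Any asymptomatic abnormality of Grade 3 or higher is a DLT.** It must also be judged related and last more than 72 hours. Shorter uncomplicated ones are expressly excluded.
- **Adding the tests would bring the escalation probability down to 0.49.** That is the formula at q = 0.30 (0.343 + 0.151), which requires every event to be seen. Day 8 and Day 15 draws see only part of them, so the figures are 0.93, 0.83 and 0.71.

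This should be corrected because it bears on a primary safety endpoint and is cheap to repair. It does not show that any dose has been wrongly cleared.

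**What to change.** Reconcile four texts: Table 7 footnote c, the pre-dose review sentence below it, the SoA chemistry row with footnote 11, and the electrolyte DLT criterion. The reconciled text should have the chemistry samples already drawn on Cycle 1 Days 8 and 15 also report calcium, magnesium and phosphorus for the remaining dose-escalation subjects, and should name the analytes that the review sentence covers.

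State also how duration will be ascertained against the protocol's own 72-hour criterion once an abnormal value is found. Section 8.2.5 asks for clinically significant values to be repeated but sets no interval, so the added tests alone would not settle duration.

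The cost is three more analytes on two existing samples per subject, with no new visit or venipuncture. The planned maximum of 42 dose-escalation subjects overstates both cost and reach: Section 4.3.1 shows that doses up to 10 mg/kg had been evaluated by September 2022, and a change now cannot recover data from subjects already assessed. No dose, DLT threshold or management rule needs to change for this measurement fix.
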